Cover page

Title: Safety and Efficacy of CO2 for Endoscopy

NCT 03287687

1/1/2020

Study Protocol:

The current literature in pediatric endoscopy does not include evidence on effectiveness and safety of CO2 insufflation in procedures besides colonoscopy and does not include children in the younger age range. Esophagogastroduodenoscopy procedures (EGDs) are much more commonly performed procedures in children so it is important to assess these clinical scenarios before adopting CO2 insufflation as the main mode of practice.

Our study aimed to address these knowledge gaps by enrolling younger children, including infants, and a wide variety of endoscopic procedures, including EGDs and percutaneous endoscopic gastrostomy (PEG) tube placement.

Study Design

This is a double-blinded, prospective, randomized study comparing CO₂ and air for insufflation during endoscopic procedures in pediatric patients performed in the Pediatric Endoscopy Unit at the University of Iowa Children's Hospital. The study was approved by the Institutional Review Board (IRB) at the University of Iowa

Subjects and Randomization

Patients aged 6 months to 21 years undergoing diagnostic or therapeutic endoscopic procedures were offered participation. These procedures included EGD, colonoscopy, PEG tube placement, and endoscopic PEG tube exchange. Exclusion criteria included non-English-speaking families needing an interpreter and patients with significant chronic lung disease, such as bronchopulmonary dysplasia, severe asthma, or cystic fibrosis. Consents and assents were obtained prior to enrollment.

Both the patient and endoscopist were blinded to the arm of study. Randomization was done by the procedure suite nurse using a sealed envelope system. To maintain allocation concealment, the nurse set up the equipment to deliver CO₂ or air then covered the relevant equipment settings

to assure complete blinding of the endoscopist and others in the room. The equipment was adjusted to deliver CO₂ or air at a similar flow rate.

Data Collection

Collected data included patient demographics (age, sex, growth parameters), procedure indication, patient's overall health status based on the American Society of Anesthesiologists (ASA) classification, endoscopy-related characteristics (duration, trainee vs faculty endoscopist and complications) and anesthesia-related parameters (duration, medication dosing, and complications). Vital signs, including EtCO₂, heart rate, respiratory rate, oxygen saturation, and blood pressure were monitored and automatically recorded continuously throughout the procedure, according to the anesthesia protocol. EtCO₂ was monitored and continuously sampled by nasal prong or via capnography for intubated patients.

Outcome Measures

Patient discomfort was assessed using 3 scales:

1. Face, Legs, Activity, Cry, and Ability to be Consoled (FLACC) behavioral assessment score
2. Global Parent Perception of Pain (PPP) scale
3. FACES scale; for neurodevelopmentally appropriate children 5 years and older.

Pain

FLACC at baseline, within 15 minutes of return to recovery area, when awake. FLACC scores categorized as no pain, mild pain, moderate to severe pain, very severe pain or worst pain ever

PPP at baseline, when awake and 4 hours post discharge. PPP scores categorized as no pain, mild pain, moderate to severe pain, very severe pain or worst pain ever

VAS at baseline, when awake and 4 hours post discharge. VAS scores categorized as no pain, mild pain, moderate to severe pain, very severe pain or worst pain ever

Abdominal girth at baseline, after procedure, at discharge, and 4 hours post discharge

Endoscopist assessment

Perceived ease of inflation: easy or average, mild difficulty, very difficult

Perceived patient discomfort: comfortable or average discomfort, above average discomfort

Endoscopist guess of inflation gas

Abdominal girth was measured by the same nurse at the level of the umbilicus before the procedure, immediately upon arrival in the recovery area after the procedure, and again just before discharge. Patients were sent home with a tape measure and a postage-prepaid response card on which they recorded the abdominal girth four hours after completion of the procedure. Parents were also asked to indicate if the patient had experienced belching, bloating or flatulence.

Sedation for all procedures was provided by an anesthesia team lead by a pediatric anesthesiologist, who was also blinded to the study group allocation. For most patients, anesthesia consisting of a continuous propofol infusion without an advanced airway such as endotracheal intubation was used. When indicated, based on the patient and procedure characteristics, general anesthesia with endotracheal intubation was occasionally used.

Data were entered into Redcap software. Adverse events defined as any undesired event occurring during endoscopy, and sedation-related complications such as hypoxia and aspiration were reported at regular intervals to the IRB during enrollment.

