#### Power calculation

The number of subjects enrolled was based on other studies, with the assumption that up to 20% of patients in the air insufflation group would report some degree of abdominal pain after endoscopy. We estimated that the frequency of reported abdominal pain in the CO2 group would be one-fourth of that (5%) seen in the air group. To accomplish this, a minimum total of 150 subjects would be needed (significance level of 5%, power of 80%) so we aimed to recruit a total of 180 patients (enrollment ratio of 1).

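### The abdominal-pain comparison pools PEG placement with the other procedures in one unadjusted test, and the power calculation makes no stated allowance for PEG wound pain that does not depend on the gas

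*Protocol*

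**What the plan says.** The Protocol's opening rationale names "percutaneous endoscopic gastrostomy (PEG) tube placement" as part of the knowledge gap the trial is meant to fill, so including these children is deliberate. Subjects and Randomization lists the eligible procedures: "These procedures included EGD, colonoscopy, PEG tube placement, and endoscopic PEG tube exchange". It describes sealed-envelope randomisation and mentions no stratification by procedure.

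The SAP's Power calculation rests on "the assumption that up to 20% of patients in the air insufflation group would report some degree of abdominal pain after endoscopy", with the CO2 rate set at "one-fourth of that (5%) seen in the air group". At a 5% significance level and 80% power it concludes that "a minimum total of 150 subjects would be needed", and it sets a recruitment target of 180 with equal allocation. The rates are attributed to other, unnamed studies.

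The Statistical Analysis Plan section compares categorical variables by chi-square or Fisher's exact test. Neither document gives an expected procedure mix, a procedure stratum or subgroup, or separate handling of PEG placement.

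**The concern.** PEG placement is percutaneous by name: it passes through the abdominal wall. Some abdominal pain afterwards is to be expected whichever gas was used, so a fourfold reduction from changing the gas is not credible in these children. The scales in Outcome Measures (FLACC, PPP, FACES/VAS) grade pain in general and do not separate a wound from distension.

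Each painful PEG placement therefore adds an event that the gas largely cannot prevent. Both arm rates rise, the difference shrinks, and the ratio moves towards 1. Because allocation is randomised, the pooled test keeps its false-positive rate. What is at stake is power, and a diluted estimate of any benefit in EGD and colonoscopy.

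**Working it through.** **1. The plan's own figure.** Inputs from the SAP, Power calculation: p₁ = 0.20, p₂ = 0.05, α = 0.05 (taken as two-sided), power 80%, ratio 1. With pooled variance and no continuity correction:

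n per arm = [1.96√(2 × 0.125 × 0.875) + 0.842√(0.20 × 0.80 + 0.05 × 0.95)]² / 0.15² = (0.917 + 0.383)² / 0.0225 ≈ 75.1, rounded up to 76, or 152 in total.

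This reproduces the stated 150. By the same approximation power is 79.9% at 75 per arm and 86.7% at 90 per arm. Exact binomial enumeration of the uncorrected chi-square gives 82.7% and 89.0%; Fisher's exact test gives 76.0% and 84.7%. The exact chi-square figures are used below.

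**2. Dilution model.** Let f be the PEG-placement share and q the PEG pain rate, equal in both arms. Neither is in the documents; both are assumptions. The plan's rates are kept for all other procedures:

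- Air: 0.20(1 − f) + qf
- CO2: 0.05(1 − f) + qf
- Difference: 0.15(1 − f)

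Example with f = 10% and q = 70%: air 0.18 + 0.07 = 25%; CO2 0.045 + 0.07 = 11.5%. The ratio falls from 4.0 to 2.2.

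| PEG share | Air vs CO2 (q = 70%) | Power, N = 150 | Power, N = 180 | N = 180, q = 50% to 100% |
|---|---|---|---|---|
| 0 | 20% vs 5% | 82.7% | 89.0% | 89.0% |
| 3% | 21.5% vs 7.0% | 74.8% | 81.9% | 83.6% to 79.6% |
| 5% | 22.5% vs 8.3% | 69.9% | 77.1% | 79.8% to 73.5% |
| 10% | 25% vs 11.5% | 58.5% | 65.7% | 70.1% to 60.4% |
| 20% | 30% vs 18% | 40.5% | 47.1% | 52.2% to 42.0% |

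**3. Share at which power reaches 80%.** At 180, all evaluable: f = 4.9% (q = 50%), 3.8% (q = 70%) and 2.9% (q = 100%). That is about 5 to 9 children (0.029 × 180 = 5.2; 0.049 × 180 = 8.8). At 150: f = 1.3%, 1.0% and 0.7%. The normal approximation is stricter: 4.0% to 2.4% at 180, and no reserve at 150.

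**4. Sample size for 80% power, pooled test (normal approximation).** At a 5% share, 188 to 216 in total; at 10%, 234 to 286 (q = 50% to 100%).

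**5. Partial gas effect.** If CO2 cut PEG pain from 70% to 60%, power at 180 would still be only 73% at a 10% share and 61% at 20%.

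**6. Alternative analyses (simulation, N = 180, q = 70%).**

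| PEG share | Pooled | Cochran-Mantel-Haenszel, PEG as its own stratum | Non-PEG only |
|---|---|---|---|
| 5% | 77% | 84% | not needed here |
| 10% | 66% | 77% | 85% |
| 20% | 47% | 62% | 81% |

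**The case against.** A reader might infer that the stated 80% power is simply not delivered. The documents do not support that. They give no PEG share and no PEG pain rate, and the Protocol's rationale describes EGD as much the more common procedure. The target is 180, not 150. At 70% PEG pain it still gives 82% power with a 3% PEG share, provided all 180 are evaluable. This objection stands, and it is why the conclusion is conditional.

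The 20% and 5% are also worded as rates for whole arms, so they could already include PEG patients. For a very small share that is possible. At a 5% share with 70% PEG pain, however, PEG alone supplies 0.05 × 0.70 = 3.5 of the 5 percentage points in the CO2 arm. The other procedures would then need (20 − 3.5)/0.95 = 17.4% against (5 − 3.5)/0.95 = 1.6%, roughly an elevenfold reduction and harder to believe than a fourfold one.

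It is tempting to argue that the rates cannot allow for PEG because the Protocol says the paediatric evidence covers only colonoscopy. The SAP does not say its source studies were paediatric, and the same argument would undermine the rates for EGD. The point here does not depend on it.

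That PEG pain is largely independent of the gas is a clinical inference from the nature of the procedure, not a statement in the documents. The SAP also does not say which scale or time point defines the sized outcome, so q cannot be fixed. The range for q and step 5 of the working are there for that reason.

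Finally, a reader might conclude that PEG placement should be removed from the comparison. Its inclusion is a stated aim, so removal would narrow the population to which the main answer applies.

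**Conclusion.** The concern holds in conditional form. The plan puts a deliberately included percutaneous procedure into a single unadjusted pain comparison and makes no stated allowance for it. Assuming 20% vs 5% in the other procedures and PEG pain of 50% to 100% unrelated to the gas, exact power at 180 drops below 80% once PEG placements pass about 3% to 5% of patients, and at 150 once they pass about 1%. At shares of 10% to 20% the loss is large: 66% to 47% at 70% PEG pain. Below the threshold, with all 180 evaluable, the plan delivers its stated power. Any missing outcomes lower the threshold, and part of the pain data is collected four hours after discharge.

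The documents support neither a flat statement that the trial is underpowered nor a requirement to exclude PEG. They do support the view that the pooled test is the weaker choice for this mix of procedures.

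**What to change.** - **SAP, Statistical Analysis Plan and Power calculation:** replace the pooled test of the sized pain outcome with one stratified by procedure, for example Cochran-Mantel-Haenszel with PEG placement as its own stratum.
- **Reporting:** give pain by arm separately for PEG placement and for procedures without a new abdominal-wall puncture. State to which group PEG exchange belongs.
- **Power:** state the expected PEG share and restate power for it. Stratifying recovers much of the loss but not all: at a 10% share and 70% PEG pain it reaches 77%, still short of 80%.
- **Other outcomes:** keep every randomised child in the EtCO2, abdominal girth and adverse-event analyses.

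The cost is a few sentences, a little more analysis and possibly a lower stated power. Restricting the sized comparison to non-PEG procedures is optional. It gives more power (85% at a 10% share) but narrows the population, and it uses up part of the margin between 150 and 180 that would otherwise cover missing outcomes.

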#### STATISTICAL ANALYSIS PLAN

Cohort demographics were analyzed using descriptive statistics. Continuous variables were summarized using the mean, and standard deviation (SD) or median and interquartile range (IQR) and compared using the Student t-test for normally-distributed data and the Wilcoxon rank-sum test for data with skewed distribution. Categorical variables were summarized using counts and frequency as a percentage and compared using Chi-Square test or Fisher's exact test. A p-value  $<0.05$  was considered statistically significant. Statistical analysis was performed with SAS 9 statistical software (SAS Institute, Cary, NC).

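### Four procedure types and ages 6 months to 21 years are compared only with unadjusted two-group tests and no estimate by procedure; the tests are valid, but a procedure-stratified analysis would serve the trial's aim better at almost no cost

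*Protocol*

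**What the plan says.** The Protocol (Subjects and Randomization) sets a wide entry: "Patients aged 6 months to 21 years undergoing diagnostic or therapeutic endoscopic procedures were offered participation". It adds: "These procedures included EGD, colonoscopy, PEG tube placement, and endoscopic PEG tube exchange". Its opening paragraphs justify this breadth by the lack of paediatric evidence on CO2 outside colonoscopy and in younger children.

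On allocation the same section states: "Randomization was done by the procedure suite nurse using a sealed envelope system". It does not mention strata, blocks, the number of sequences or how they were generated.

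The SAP (Statistical Analysis Plan) gives the tests. Continuous variables are "compared using the Student t-test for normally-distributed data and the Wilcoxon rank-sum test for data with skewed distribution". For pain categories: "Categorical variables were summarized using counts and frequency as a percentage and compared using Chi-Square test" or Fisher's exact test. The SAP text reviewed contains no stratified or covariate-adjusted analysis and no estimate by procedure or age.

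The SAP (Power calculation) uses one pain rate per arm: "up to 20% of patients in the air insufflation group would report some degree of abdominal pain after endoscopy", and a CO2 rate that "would be one-fourth of that (5%) seen in the air group".

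The Protocol (Data Collection) lists age and procedure indication among the data collected, but does not name procedure type.

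**The concern.** The four procedures are unlikely to carry the same risk of pain afterwards, and raw abdominal girth plainly depends on age in a sample running from infants to young adults. A factor known before randomization that predicts the outcome can be used in the analysis; here none is.

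Two things are at stake:

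- **Precision.** If pain rates differ by procedure, the pooled comparison carries avoidable noise, and an arm that by chance receives more of the painful procedures is not corrected for.
- **The trial's own question.** A pooled result could be driven largely by one procedure. With no by-procedure estimate planned, the gap the Protocol sets out to fill is not addressed directly, and any such estimate produced later would be post hoc.

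**Working it through.** **Inputs from the documents.** Pain 20% (air) vs 5% (CO2), 5% significance, 80% power, minimum 150, target 180, ratio 1 (SAP, Power calculation). Two-sided testing is assumed. The documents give no procedure shares and no pain rates by procedure, so those below are assumptions.

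**1. The plan's own figure.** With pooled rate (0.20 + 0.05)/2 = 0.125:

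n per arm = [1.960·√(2·0.125·0.875) + 0.842·√(0.20·0.80 + 0.05·0.95)]² / 0.15² = (0.917 + 0.383)² / 0.0225 ≈ 75.1, so 76 per arm and 152 in total.

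The stated 150 reproduces. The same formula gives 79.9% power at 75 per arm and 86.7% at 90 per arm.

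**2. Chance imbalance without stratification.** If a procedure makes up 30% of 180 patients, the between-arm difference in its share has SD √(0.3·0.7·2/90) = 6.8 points. A gap of 10 points or more is 10/6.83 = 1.46 SD, probability 14%; the exact hypergeometric calculation also gives 14%. For other shares the exact probability is:

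| Share of patients | P(gap ≥ 10 points) |
|---|---|
| 10% | 2% |
| 20% | 9% |
| 30% | 14% |
| 50% | 18% |

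**3. What such a gap does.** The shift in the observed pain difference is the gap times the contrast in pain rates:

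- 30% vs 10%: 0.10·0.20 = 2.0 points
- 40% vs 15%: 0.10·0.25 = 2.5 points
- 60% vs 10%: 0.10·0.50 = 5.0 points

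The planned difference is 15 points. Given a gap of exactly 10 points (35% vs 25%), the type I error of the unadjusted test is 5.7% to 8.1% over these contrasts. Averaged over all randomizations it is 4.8% to 5.1%, and the mean difference stays at 15.0 points.

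**4. Power at the planned effect.** Simulation with 90 per arm, unstratified 1:1 allocation and three procedure groups of 70/20/10% (assumed). Air rates average to 20%: 0.7·12 + 0.2·30 + 0.1·56 = 20, and 0.7·8 + 0.2·30 + 0.1·84 = 20. In each case a common odds ratio is chosen so that the CO2 rate averages 5%.

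| Air-arm pain by group | Pooled chi-square | Stratified CMH |
|---|---|---|
| 20/20/20% | 89% | 88% |
| 12/30/56% | 89% | 91% |
| 8/30/84% (extreme) | 89% | 96% |

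The simulated 89% is slightly above the 86.7% from the formula, which is a normal approximation. A second set of assumptions (two groups, constant risk ratio 0.25, N = 180) agrees: pooled power is 89% throughout, and CMH after unstratified allocation gives 89%, 90%, 91% and 93% as heterogeneity grows.

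**5. If the envelopes were in fact stratified.** The pooled chi-square then becomes conservative. In the two-group simulations at N = 180 with differing pain rates its type I error is 2.2% to 4.3%, while CMH stays at about 5%. The analysis point therefore holds whichever way allocation was done.

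**6. Events available.** 90·0.20 + 90·0.05 = 22.5, so about 22 pain events are expected in all. That supports three strata, not many covariates, and leaves few events per procedure group.

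**The case against.** An unadjusted primary analysis of a randomized trial is legitimate, and adjustment is an efficiency gain rather than a repair. The stated sample size reproduces, and 180 patients give margin over 80% power. About 22 events across three procedure groups cannot settle the effect outside colonoscopy. All of this stands, and it limits the point to a modest improvement.

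Four stronger readings are tempting and not supported:

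- **That a single unstratified sequence was used.** A reader might infer this from the Protocol's silence. The documents do not say whether allocation was stratified or blocked; that is a reporting gap, not a demonstrated design fault.
- **That imbalance biases the comparison.** Under proper randomization the unadjusted estimate is correct on average and the test keeps its error rate. What remains is lost precision and a possible shift in one particular trial.
- **That the trial is seriously underpowered.** Fixing the odds ratio at 0.30 in the 8/30/84% case gives 46% (pooled) vs 61% (CMH). The overall CO2 rate is then about 10%, not the planned 5%, so most of the fall comes from a smaller effect. At the planned effect pooled power is 89%.
- **That separate envelope sets should be introduced.** The Protocol describes enrolment and randomization in the past tense, so there is little basis for changing allocation.

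It can also fairly be said that procedure may not be prognostic, since the documents give no rates by procedure. In that case adjustment costs under 1 point of power.

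**Conclusion.** The point holds as an inexpensive improvement to the analysis. The planned tests are valid and the sample size is not invalidated. They do give up some precision when pain differs by procedure: nothing with no heterogeneity, about 2 points of power in the moderate case and about 7 in a deliberately extreme one. They also leave uncorrected a chance imbalance that reaches 10 points in about 14% of trials for a procedure with a 30% share. These sizes rest on assumed procedure shares and pain rates. Two parts need no such assumption: the SAP text plans no estimate by procedure although evidence beyond colonoscopy is the stated purpose, and the documents do not report whether allocation was stratified.

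**What to change.** - State in the Protocol how the envelope sequence was generated and whether it was stratified or blocked.
- List procedure type explicitly among the data collected.
- In the SAP, analyse any-pain by a CMH test with a common odds ratio, stratified by procedure group: EGD only, any colonoscopy, PEG placement or exchange.
- Include procedure group and age in the models for girth and EtCO2.
- Report the arm difference with a confidence interval for each procedure group, labelled descriptive.

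The cost is SAP wording and one data field. The downside is under 1 point of power if procedure is not prognostic, and by-procedure intervals that will be wide. All factors used are known before randomization, so the allocation procedure need not change.

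### The planned tests for the endoscopist ratings use neither the recorded operator grade nor the order of the ease-of-inflation levels: they stay valid but give up power

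*Protocol*

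**What the plan says.** The protocol (Data Collection) lists among the recorded items "endoscopy-related characteristics (duration, trainee vs faculty endoscopist and complications". Under Outcome Measures, in the endoscopist assessment, two ratings follow: "Perceived ease of inflation: easy or average, mild difficulty, very difficult" and "Perceived patient discomfort: comfortable or average discomfort, above average discomfort". The first has three ordered levels, the second has two.

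The SAP (Statistical Analysis Plan section) has one rule for all such data: "Categorical variables were summarized using counts and frequency as a percentage and compared using Chi-Square test or Fisher's exact test". It names no stratified, rank-based or covariate-adjusted method for categorical data and gives operator grade no part in any outcome comparison. It does not say whether the three levels are to be collapsed.

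The protocol (Subjects and Randomization) describes allocation thus: "Randomization was done by the procedure suite nurse using a sealed envelope system". No stratification factor is mentioned. On blinding it says: "Both the patient and endoscopist were blinded to the arm of study". The Power calculation section of the SAP sizes the trial on abdominal pain and says nothing about the endoscopist ratings.

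**The concern.** How easily the bowel inflates is a personal judgement and may depend on the experience of whoever holds the endoscope. If trainees and faculty report difficulty at different rates, that difference stays in the error term of an unstratified test although the variable that would remove it is already collected.

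Separately, a general chi-square or Fisher test on a three-level table treats the levels as unordered. It spends two degrees of freedom where a shift towards easier or harder inflation needs one.

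Ease of inflation is the listed outcome that rates how the gas performs for the operator, and the protocol presents the study as evidence needed before CO2 becomes routine. At stake is the chance of detecting a real difference on that outcome, not the validity of the comparison.

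**Working it through.** **1. The plan's own figure.** From the SAP: 20% versus 5%, 5% significance (two-sided assumed), 80% power, 1:1. With pooled variance and no continuity correction, the mean rate is 0.125 and

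n per arm = [1.96·√(2·0.125·0.875) + 0.842·√(0.20·0.80 + 0.05·0.95)]² / 0.15² = (0.917 + 0.383)² / 0.0225 ≈ 75.1, rounded up to 76.

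The total of 152 agrees with the stated minimum of 150; 75 per arm gives 79.9% power. This figure concerns abdominal pain. There is no corresponding figure for the ratings.

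**2. Assumed inputs.** The documents give no trainee share, difficulty rate or expected effect on ease of inflation. Assumed: 90 per arm (from the target of 180), trainee share 30% to 50%, odds ratio 0.35 for CO2 versus air, and the air-arm difficulty rates shown below.

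**3. Gain from stratifying (any difficulty versus none).** Simulated trials were tested in two ways at two-sided 5%:
- unstratified: z = (p_A − p_C) / √[p̄(1 − p̄)·2/n];
- Cochran-Mantel-Haenszel: z = Σ(a − n_A·m/N) / √Σ[n_A·n_C·m(N − m) / (N²(N − 1))], summed over the trainee and faculty strata, where a is the number of difficult cases in the air arm, m is the stratum total of difficult cases and N is the stratum size.

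| Faculty/trainee difficulty with air | Trainee share | Unstratified | Stratified |
|---|---|---|---|
| 25%/25% | 50% | 73% | 73% |
| 10%/20% | 30% | 47% | 47% |
| 15%/40% | 50% | 73% | 75% |
| 10%/40% | 50% | 67% | 72% |
| 10%/50% | 50% | 70% | 76% |

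Repeat runs moved these by about a point. With the effect set instead so that power is near 80% (trainee share 20% to 50%), stratifying added 0 to 1.5 points when the two grades differed by 10 to 20 points, and 2 to 3 points when they differed by 30.

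The gain is modest because operator grade explains little of the variance. That share is q(1 − q)(p_T − p_F)² / [p(1 − p)], with q the trainee share and p the overall rate. For 15%/40% with half trainees it is 0.25·0.0625 / (0.275·0.725) = 7.8%. For 10%/50% it is 0.25·0.16 / (0.30·0.70) = 19%.

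**4. Gain from using the order (three levels).** Further assumption: 30% of air-arm difficulty falls in the top level.

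| Faculty/trainee difficulty with air | Trainee share | Three-level chi-square | Unstratified rank test | Van Elteren |
|---|---|---|---|---|
| 10%/20% | 30% | 35% | 47% | 47% |
| 15%/40% | 50% | 63% | 74% | 77% |
| 10%/50% | 50% | 60% | 71% | 77% |

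The total gains are 12, 14 and 17 points; across runs, about 11 to 17. The step from chi-square to rank test supplies 12, 11 and 11 of those points. Stratification supplies 0, 3 and 6.

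If the three levels were collapsed to any difficulty versus none, most of the ordering loss would vanish. At 15%/40% that test has 73% power, so van Elteren would gain about 77 − 73 = 4 points.

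**5. Validity and chance imbalance.** With no gas effect, the unstratified and Mantel-Haenszel tests each rejected in 4.8% to 5.1% of trials in every setting. The SD of the difference in trainee share between arms is √[2q(1 − q)/90]: 6.0 points at q = 0.2 and 7.5 at q = 0.5. A gap above 10 points therefore has probability 9% to 18%. At 15%/40%, a 10-point gap shifts the difference by 0.10 × 25 = 2.5 points, against a standard error of √(2·0.275·0.725/90) = 6.7 points, or under 0.4 standard errors.

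**The case against.** The best case for the plan is that an unadjusted comparison is legitimate in a blinded randomised trial, that these ratings did not size it, and that every rate behind the gains is assumed. Operator grade is also only one candidate covariate: procedure type and age (6 months to 21 years) could matter as much. All of this stands, and it keeps the priority low. It does not answer the loss from ignoring the order of the levels, which does not depend on operators differing.

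Three stronger readings are tempting, and the documents support none of them.
- *Uneven numbers of trainees would create a spurious difference between arms.* Chance imbalance is already covered by the 5% error rate. It can shift one realised trial a little (step 5), but it is not bias.
- *Operator grade is a strong rater effect.* No trainee-faculty contrast is given. Because the lowest level takes in average ease, trainees judging against their own norm might differ little from faculty.
- *The ratings come from both trainees and faculty.* The protocol records the grade of the endoscopist but not who completes the assessment when a trainee operates. If faculty always rate, operator grade could still matter through handling of the endoscope, but the case for stratifying is weaker.

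An analysis by individual rater is not supported either, since rater identity is not among the listed data.

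**Conclusion.** The point holds as a matter of efficiency. The planned tests are valid at 5%, but they use neither a recorded variable nor the order of the levels. Under the assumed rates, stratifying is worth about 0 to 6 points of power and costs nothing appreciable when operators do not differ. A stratified rank test is worth about 11 to 17 points over a chi-square on all three levels, mostly through the ordering.

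The larger figure applies only if the three levels are tested as they stand, which the SAP leaves open. Both ranges depend on the assumed odds ratio, difficulty rates and trainee share. The abdominal-pain comparison that sized the trial is not affected.

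**What to change.** In the Statistical Analysis Plan section of the SAP, replace the general rule for these two outcomes:
- ease of inflation, all three levels: van Elteren (stratified Wilcoxon) test;
- endoscopist-rated discomfort, two levels: Cochran-Mantel-Haenszel test;
- both stratified by the recorded trainee or faculty status. The documents do not say when this is recorded; define it as the status set before allocation where the record allows, because a handover prompted by difficulty could itself depend on the gas.

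In the protocol's endoscopist assessment, state who gives the rating when a trainee performs the procedure.

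The SAP is written in the past tense. If the analysis has already been run, keep the chi-square or Fisher result as planned and label the stratified version a sensitivity analysis.

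The cost is wording and a little more analysis on an outcome that did not size the trial. No new data item is needed for the stratification. If operators differ little, the benefit is almost entirely from the ordering.

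### EtCO2 is sampled by two routes, and the SAP's unadjusted tests, if applied to it, leave any level difference between routes in the error variance: a modest, avoidable loss of precision

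*Protocol*

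**What the plan says.** **Measurement.** The protocol (Data Collection) lists EtCO2 with the other vital signs, recorded automatically during the procedure. It was "continuously sampled by nasal prong or via capnography for intubated patients".

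**Who gets which route.** The sedation paragraph near the end of the protocol states: "For most patients, anesthesia consisting of a continuous propofol infusion without an advanced airway such as endotracheal intubation was used". It continues: "When indicated, based on the patient and procedure characteristics", "general anesthesia with endotracheal intubation was occasionally used". No intubated share is given. The anesthesia team was led by an anesthesiologist blinded to allocation.

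**Allocation.** The protocol (Subjects and Randomization) says "Randomization was done by the procedure suite nurse using a sealed envelope system". It states no stratification by airway or procedure.

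**Analysis.** The SAP (Statistical Analysis Plan) has continuous variables "compared using the Student t-test for normally-distributed data and the Wilcoxon rank-sum test for data with skewed distribution". The SAP text available contains no covariate, stratum or model. It does not name EtCO2, and it does not say which value from the continuous recording (peak, mean, change) would be compared.

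**The concern.** Readings from two sampling routes, taken under two breathing situations, would enter one two-group comparison. If the routes read at different levels, that difference is a source of variation which a model could remove and a plain t-test cannot. Route also follows patient and procedure characteristics, so it carries some case mix with it.

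The trial's title puts safety first, and EtCO2 is the recorded variable that bears most directly on whether insufflated CO2 is absorbed. What is at stake is the width of the interval around the EtCO2 difference between arms. A second issue is that any effect of CO2 on the reading might differ between intubated and non-intubated patients, and a single overall mean would not show it. The documents neither establish nor exclude such a difference.

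**Working it through.** **1. The plan's own figure.** The only sample-size figure concerns pain: 20% against 5%, 5% significance, 80% power, at least 150 in total. Two-sided, pooled variance, no continuity correction:

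n per arm = [1.960·√(2·0.125·0.875) + 0.842·√(0.20·0.80 + 0.05·0.95)]² / 0.15² = 75.1, rounded up to 76.

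That is 152 in total, which agrees with 150. It does not bear on EtCO2, for which the documents give no SD, target difference or power.

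**2. Inputs for EtCO2.**
- From the SAP (Power calculation): 180 patients, ratio 1, so 90 per arm.
- Assumed: intubated share f, described only as occasional.
- Assumed: offset g between route means, in units of the within-route SD. No text says that the routes read differently.

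**3. Variance left in by ignoring route.** Variance factor = 1 + f(1 − f)g². Effective n = 180 / factor. For scale, take the difference that has 80% power at 90 per arm once route is removed: (1.960 + 0.842)·√(2/90) = 0.418 SD. The last column gives the power of the unadjusted test for that difference.

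| f | g | Variance factor | Effective n | Power |
|---|---|---|---|---|
| 5% | 0.5 | 1.012 | 178 | 79.5% |
| 5% | 1 | 1.048 | 172 | 78.2% |
| 10% | 0.5 | 1.0225 | 176 | 79.1% |
| 10% | 1 | 1.090 | 165 | 76.5% |
| 20% | 1 | 1.160 | 155 | 73.9% |
| 20% | 1.5 | 1.360 | 132 | 67.1% |
| 20% | 2 | 1.640 | 110 | 59.0% |

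The first four rows fit occasional intubation and a moderate offset. The last three show what it takes for the loss to become material through a higher share; at 5-10% intubated, a 2 SD offset also brings power down to 72.8% and 67.1%.

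**4. Does ignoring route bias the test?** The unadjusted t-test was simulated 20,000 times per setting, with no arm effect, 90 per arm and intubation independent of arm. It rejected in 5.1% of trials (f = 10%, g = 1) and 5.3% (f = 20%, g = 2). The error rate stays close to nominal because the standard error already allows for chance imbalance in airway.

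**5. How much can results by route show?** The 95% half-width for the intubated group, in within-route SDs, is t·√(1/n₁ + 1/n₂).
- 5% intubated: 9 patients, 4 against 5: 2.365·√(1/4 + 1/5) = ±1.6 SD.
- 10% intubated: 18 patients, 9 against 9: 2.120·√(2/9) = ±1.0 SD.

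**The case against.** **EtCO2 is not a listed outcome.** A reader might infer that it is the trial's main safety measure. The documents do not say so: it stands among the vital signs under Data Collection and is absent from Outcome Measures, and the safety reporting described is of adverse events and sedation complications. This stands, and it limits the weight of the point.

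**Pooling is not stated.** A reader might also infer that the SAP prescribes one pooled EtCO2 test. That is only the consequence of applying its general rule, since the SAP text available never mentions EtCO2. The undefined summary measure is the prior gap, and the choice matters: in a change score, a constant route offset cancels.

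**Randomization protects the comparison.** It is tempting to say that uneven intubation could mimic or hide a CO2 effect. As a claim of bias this fails, as step 4 shows. Only a precision loss remains.

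**The size is assumed.** Both inputs are missing from the documents, and at the low end the loss is about 1%. The calculated gain also cannot be credited wholly to a route term in a model that includes a baseline EtCO2 taken by the same route, because the baseline absorbs part of the offset.

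**Adjustment is not quite free.** Airway route and a pre-insufflation value are not separate items in the protocol's data list. Intubated numbers are small. A linear model would displace the SAP's provision for skewed data. Blinding alone does not show that airway was settled before insufflation. These points change the form of the fix. They do not remove the benefit of adjusting for a factor that arm should not affect.

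**Conclusion.** The concern holds as a minor point about precision. Two routes are documented, and the SAP's stated methods have no means of removing a difference between them. If 5-10% of patients are intubated and the routes differ by 0.5-1 SD, variance is about 1-9% higher than it need be: 180 patients do the work of about 178 to 165, and power against a 0.418 SD difference falls from 80% to between 79.5% and 76.5%. Larger losses need a higher intubated share or a larger offset. All of this rests on those two assumed quantities and on an offset existing at all.

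The documents do not support reading this as a flaw in the validity of the EtCO2 comparison, as the failure of a designated safety endpoint, or as a missed power target, since the trial was sized on pain alone.

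**What to change.** - Name the EtCO2 summary to be compared. Analyse it with a linear model containing arm, airway route at the start of the procedure (nasal prong or intubated) and the first recorded pre-insufflation EtCO2 where available. Taking the route at the start keeps the covariate free of anything that happens after insufflation.
- If the data are skewed, use a transformed or rank-based version, so that the SAP's provision for skewed data is kept.
- Report the arm difference with its 95% CI for each route, labelled descriptive. With an intubated interval of about ±1.0 to ±1.6 SD, the absence of a visible difference between routes should not be read as evidence that there is none.
- If the unadjusted comparison has already been made, show the adjusted result beside it and mark it as added.

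**Cost.** A few lines in the SAP, and extraction of airway route and the early EtCO2 value from the anesthesia record. That both can be found there is a reasonable expectation, but the protocol does not state it. No further patients, visits or measurements are needed.
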